## Introduction

### Background and rationale

Pleural effusion is a common finding in patients admitted with acute heart failure and congestion, and patients with larger heart failure-related pleural effusion necessitating therapeutic thoracentesis (from here on only referred to as thoracentesis) have high mortality rates [1,2]. The current treatment options for heart failure-related pleural effusions are decongestion with diuretics in combination with initiation or adjustment of guideline-directed medical therapy (GDMT) for the underlying heart failure condition, and for larger effusions, thoracentesis is an option. However, thoracentesis in heart failure-related pleural effusions is controversial. There is no evidence from randomised trials, and there is no recommendation in international guidelines [3,4]. The timeliness and benefits of thoracentesis have not previously been studied.

### Study objectives

#### Primary objective

To investigate if a strategy of referral to up-front thoracentesis in addition to pharmacological therapy compared with pharmacological therapy alone increases the number of days alive outside of the hospital during the following 90 days in patients with pleural effusion due to acute heart failure and left ventricular ejection fraction (LVEF)  $\leq 45\%$ .

#### Research hypothesis

A strategy of referring patients with heart failure-related pleural effusion to upfront thoracentesis by pigtail catheter insertion increases the number of days alive outside of the hospital during the following 90 days.

#### Secondary objectives

To determine the effectiveness of a strategy of referral to upfront thoracentesis in addition to pharmacological therapy compared with pharmacological therapy alone on admission duration, dose of

diuretics, weight loss, mortality, complications, and patient-reported outcomes such as patient satisfaction and quality of life.

## Study Methods

### Study design

The TAP-IT trial is an investigator-initiated, pragmatic, multicentre, randomised, parallel-group, open-label, controlled trial. Treatment allocation is 1:1. Participants in the intervention group are assigned to referral to upfront pigtail catheter insertion (thoracentesis) combined with standard pharmacological therapy (diuretics and GDMT). Participants in the control group are assigned to standard pharmacological therapy alone (comparator). Physicians, investigators, and participants are not blinded to the result of the randomisation.

### Randomisation

Participants are randomised with an internet-based electronic case report form and randomisation program. Randomisation is stratified according to site and whether participants are treated with oral anticoagulation therapy (regardless of type: Direct-acting oral anticoagulant or Vitamin K antagonist vs. no anticoagulation) with alternating block sizes to reduce predictability.

### Sample Size

For estimation of sample size, we assumed a t-test of superiority and found a total of 126 participants required to detect a difference of three days in the primary endpoint with an  $\alpha$  of 0.05 and a power of 90%. This assumes, that participants assigned to a strategy with referral to up-front thoracentesis in addition to pharmacological therapy will have 85 days alive and not hospitalised during the 90 days after randomisation, while participants assigned to pharmacological therapy alone will have 82 days, with a shared standard deviation of 5 days, and in-hospital mortality of 5% in both groups [5–7]. For analysis of the primary endpoint, we will assess the Mann-Whitney parameter for days alive without hospitalisation during the 90 days following randomisation, using the Wilcoxon-Mann-Whitney-test [30]. The loss of power with the Wilcoxon rank sum test compared to the t-test is often limited if distributions are normal, and when normality is violated, the Wilcoxon rank sum test can be three or four times more powerful than the independent samples t-test [31,32]. The power of 90% will allow for a possible small loss of power from using the Wilcoxon-Mann-Whitney test.

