### Statistical principles

All outcomes are tested for superiority. A two-sided p-value  $<0.05$  is considered statistically significant, and a 95% confidence interval (CI) is reported for all effect estimates. No multiplicity adjustment will be applied.

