## Primary outcome definition

Number of days alive outside of the hospital during the 90 days following randomisation. The outcome is countable with a minimum value of 0 and a maximum of 90. In case of death before the end of follow-up, the participant will be assigned the number of days they were outside of the hospital until death occurred. If the participant dies during the index admission, they will be assigned 0 days alive and outside of the hospital (Auriemma et al., 2021; Granholm et al., 2023). We anticipate 95% of participants to be discharged from the hospital [5–7] and based on limited previous observation data in patients with heart failure-related pleural effusion necessitating thoracentesis, we anticipated 78-91% of participants to survive 30 days after hospitalisation [1,2].

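### The planning values of 85 and 82 days (SD 5) for all assigned participants do not fit the SAP's own scoring rule and its anticipated 78-91% 30-day survival

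*SAP*

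**What the plan says.** The Sample Size section plans on participants assigned to thoracentesis who "will have 85 days alive and not hospitalised during the 90 days after randomisation". For the control arm it plans on 82 days, and it takes an SD of 5 days for both arms. It adds an in-hospital mortality of 5% in both groups. On this basis "we assumed a t-test of superiority and found a total of 126 participants required to detect a difference of three days", with an alpha "of 0.05 and a power of 90"%. The test is two-sided (Statistical principles: "A two-sided p-value" below 0.05) and "Treatment allocation is 1:1" (Study design).

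The section Primary outcome definition gives a range of 0 to 90 days. For a death before the end of follow-up, "the participant will be assigned the number of days they were outside of the hospital until death occurred"; a death during the index admission scores 0. The same section expects 95% to be discharged and, from data it calls limited, "we anticipated 78-91% of participants to survive 30 days after hospitalisation". Under Analysis datasets, the primary analysis covers everyone who consented and was randomised.

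**The concern.** The planning values sit in a t-test calculation with an SD, so they read as means, and they are stated for participants as assigned. The scoring rule makes every early death costly: whoever dies within 30 days scores at most 30. The survival range therefore caps the mean of an arm, and the SAP never sets that cap beside 85 and 82.

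The sample size relies on these values. If they do not describe the outcome as it will be scored in everyone randomised, the stated 90% power does not apply to the planned analysis. A reader also cannot judge whether 3 days was a realistic target. An observed mean well below 82 would look like a surprise, although the SAP's own survival figures predict it.

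**Working it through.** **1. The SAP's own figure.** For a difference of 3, SD 5, two-sided 0.05, power 90% and 1:1 allocation, the normal approximation gives 59 per arm (118 in total). The exact t-test gives 60 per arm (120). Adding 5% gives 120 × 1.05 = 126 (or 120/0.95 = 126.3). Dividing by a Wilcoxon efficiency of 0.955 gives nearly the same, 125.7. The SAP does not say which step it took, but 126 follows from its inputs.

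**2. Ceiling on the all-participant mean.** Let s be 30-day survival. A survivor scores at most 90 and an early death at most 30. This holds whether the 30 days run from admission or from discharge, because days in the index stay do not count.

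- Without the zero rule: 90s + 30(1 − s) = 30 + 60s.
- With 5% index-admission deaths scored 0: 90s + 30(0.95 − s) = 28.5 + 60s.

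| | s = 78% | s = 91% | s needed for 85 | s needed for 82 |
|---|---|---|---|---|
| No zero rule | 76.8 | 84.6 | 55/60 = 91.7% | 52/60 = 86.7% |
| 5% scored 0 | 75.3 | 83.1 | 56.5/60 = 94.2% | 53.5/60 = 89.2% |

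These ceilings favour the plan. They assume no hospital day after randomisation, no readmission, no death after day 30, and every other early death falling on day 30.

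**3. Adding hospital days.** The SAP gives no planned length of stay, so L days per person not scored 0 is an assumption, shown for 3, 5 and 7. The ceiling with the zero rule is s(90 − L) + (0.95 − s)(30 − L).

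| L | s = 78% | s = 91% |
|---|---|---|
| 3 | 72.5 | 80.3 |
| 5 | 70.6 | 78.4 |
| 7 | 68.7 | 76.5 |

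If the 30 days run from discharge, early deaths do not lose L, and the ceiling rises by L(0.95 − s); at L = 5 that is 0.2 day at 91% and 0.85 at 78%. At 91% survival, a mean of 82 leaves (83.1 − 82)/0.95 = 1.2 hospital days per person not scored 0, or 84.6 − 82 = 2.6 without the zero rule.

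**4. Discharged participants only.** The ceiling is (28.5 + 60s)/0.95, which is 79.3 at 78% and 87.5 at 91%. A mean of 85 needs s of at least (80.75 − 28.5)/60 = 87.1%, and 82 needs (77.9 − 28.5)/60 = 82.3%, both with no hospital days.

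**5. The SD.** Take 5% zeros and give everyone else the same score. An overall mean of 85 then needs 85/0.95 = 89.5 in the rest, and the SD is 89.5 × √(0.05 × 0.95) = 19.5. For 82 it is 86.3 × 0.218 = 18.8. An SD of 5 therefore cannot describe all participants once 5% score 0.

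**6. What this does to the planned test.** Suppose 85 v 82 with SD 5 holds in survivors only, and deaths are equal in both arms. In a simulation with 63 per arm, survivors had normal scores, 5% scored 0, and any further early deaths were spread evenly over 0 to 30 days. The power of the two-sided Wilcoxon-Mann-Whitney test was about 82% with the 5% zeros alone, 75% at 91% survival and 50% at 78%. Capping scores at 90 moves these by no more than about two points. With no deaths the same set-up gives about 90%.

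**The case against.** The strongest defence is that 85 and 82 describe discharged participants. The 5% in-hospital mortality is listed as a separate assumption, and 126 equals the t-test's 120 plus 5%, as if index deaths had been added on top. On that reading 85 is not impossible: it fits from 87.1% survival and 82 from 82.3%, so 82 fits over about two thirds of the range. This stands as a possible reading, but the SAP does not state it. At 91% it leaves about 2.5 hospital days for 85 and 5.5 for 82. It also does not rescue the 90% power, because the analysis includes the deaths.

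Other points have partial force. The survival range is hedged and not given by arm. Without the zero rule the shortfall at 91% is only 0.4 day, and the average of the two planning values, 83.5, lies below 84.6; with the zero rule it exceeds 83.1. Rounding does not help: 91.49% survival gives at most 84.9. If the range applied only to those discharged, the ceiling would be lower still, 0.95(30 + 60s) = 73.0 to 80.4. As medians 85 and 82 would be possible, but a t-test with an SD uses means.

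It is also correct that moving the means alone leaves a t-test's N, power and detectable difference unchanged, and that the planned primary test does not compare means.

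A reader might infer that the values were taken from general acute heart failure cohorts and describe a healthier population. The documents do not show this: the citations follow the 5% mortality figure, and nothing traces 85 and 82 to them. Nor is 126 miscalculated. A t-test with an SD of 19.5 would need about 1,776 participants, but that cannot be read as the required size here, because Wilcoxon-Mann-Whitney power depends on the shape of the distribution.

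**Conclusion.** The inconsistency is real and lies within the SAP's own figures. For everyone randomised, 85 days exceeds the ceiling at every survival value in the stated range, by 0.4 to 8.2 days without the zero rule (85 − 84.6 and 85 − 76.8) and by 1.9 to 9.7 with it (85 − 83.1 and 85 − 75.3). A mean of 82 is reachable only near the top of the range with almost no hospital days, and is out of reach below about 89% survival (87% without the zero rule). Reading the values as those of discharged participants removes the impossibility for part of the range, but then they do not describe the analysed outcome.

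The ceilings rest only on the SAP's survival range, its scoring rules and its 5% in-hospital mortality. The power figures rest further on assumed normal scores in survivors, equal deaths in both arms and an assumed timing of early deaths. They show the direction and rough size of the loss; they are not a replacement power statement. The finding is that the two sections must be reconciled.

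**What to change.** In the Sample Size section:

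- State which participants 85, 82 and SD 5 describe.
- Add arm values for all participants that follow from the scoring rule, the 78-91% survival range and a stated range of index stay.
- Restate the power or detectable difference of the Wilcoxon-Mann-Whitney test for the planned 126 from that full outcome distribution, deaths included, with the assumed split of deaths between arms. Changing the means alone would alter nothing.
- Keep the present figures as the historical basis of the sample size.

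No increase in sample size is requested, and the primary analysis does not change. The cost is some SAP wording and a short simulation. The drawback is that the stated power becomes less favourable.

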## Statistical methods

### Analysis datasets

The primary analysis will be on the **full analysis dataset**, including all participants from whom written informed consent is obtained and randomised. Subjects will be analysed according to their allocated treatment group according to the intention-to-treat principle.

Exploratory analyses will be performed on the per-protocol and the as-treated datasets as defined below. The **per-protocol dataset** includes participants that followed the treatment strategy according to the

protocol (patients in the intervention arm being referred to upfront thoracentesis by the treating physician (scheduling when the thoracentesis will be performed) and patients in the control arm who are not referred to thoracentesis within five days after randomisation). The **as-treated dataset** is defined as participants who received the planned treatment according to the allocated treatment strategy (thoracentesis performed on participants in the interventional group and thoracentesis not performed on participants in the control group).

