### Statistical methods to compare primary and secondary outcomes between groups

#### Main analysis of primary outcome

The primary outcome of the trial, “days alive without hospitalisation during the 90 days following randomisation”, is a countable outcome with an anticipated non-normal distribution.

Accordingly, we plan a non-parametric analysis of the primary outcome [16]. We will assess the Mann-Whitney parameter using the Wilcoxon-Mann-Whitney-test on the full analysis dataset according to the intention-to-treat principle [17].

For explorative purposes, the analysis will also be performed on the per-protocol dataset and as-treated dataset.

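### The 90% power assumes an SD of 5 days, which the primary endpoint cannot have once 5% in-hospital deaths are scored 0; power for the planned test is unsupported

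*SAP*

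**What the plan says.** SAP, Sample Size: a superiority t-test with α 0.05 and 90% power gives 126 participants for a three-day difference in the primary endpoint, 85 against 82 days, "with a shared standard deviation of 5 days, and in-hospital mortality of 5% in both groups". The same section notes that the primary analysis will be a Wilcoxon-Mann-Whitney test, argues that this test loses little under normality and can gain otherwise, and concludes: "The power of 90% will allow for a possible small loss of power from using the Wilcoxon-Mann-Whitney test".

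SAP, Primary outcome definition: the scale runs from 0 to 90. "If the participant dies during the index admission, they will be assigned 0 days alive and outside of the hospital". For a later death, "the participant will be assigned the number of days they were outside of the hospital until death occurred". On expected mortality: "We anticipate 95% of participants to be discharged from the hospital", and "we anticipated 78-91% of participants to survive 30 days after hospitalisation".

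SAP, Analysis datasets: the primary analysis uses the full analysis dataset, "including all participants from whom written informed consent is obtained and randomised". SAP, Main analysis of primary outcome: the endpoint "is a countable outcome with an anticipated non-normal distribution" and is compared by the Wilcoxon-Mann-Whitney test under intention to treat.

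**The concern.** The sizing names two inputs together, an SD of 5 and 5% in-hospital mortality, that cannot both describe an endpoint on which those deaths score 0. The deaths are outcome values in the primary analysis, not missing data. The only allowance the section makes is for changing from a t-test to a rank test. It makes none for a cluster of deaths at the bottom of the scale, which carries no treatment contrast if mortality is equal in the arms.

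This is the SAP's only power statement for its primary hypothesis. Anyone weighing a null result would take 90% as the chance of having detected three days, although that figure was not calculated for the endpoint or the test in use.

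**Working it through.** **Reproducing 126.** Inputs from Sample Size and Statistical principles: difference 3, SD 5, two-sided α 0.05, power 90%, 1:1 allocation. The standardised difference is 3/5 = 0.6. The noncentral t calculation gives 59.35 per arm, so 60 per arm and 120 in total. A 5% inflation gives 120 × 1.05 = 126, or 59.35/0.95 = 62.5, so 63 per arm. The stated 126 is therefore consistent with treating the 5% as attrition, though the SAP does not describe that step. With SD 5 and no deaths, t-test power at 63 per arm is 91.6%.

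**SD of the endpoint with 5% scored 0.**

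- If 85/82 and SD 5 describe survivors, SD = √(0.95 × 5² + 0.05 × 0.95 × mean²). For 85: √(23.75 + 343.19) = 19.2. For 82: √(23.75 + 319.39) = 18.5.
- If 85/82 are means over everyone, the smallest possible SD is mean × √(0.05/0.95): 19.5 for 85 and 18.8 for 82.
- Conversely, SD 5 requires p/(1 − p) ≤ (5/mean)², so at most 0.35% zeros for 85 and 0.37% for 82.

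**Could SD 5 describe everyone discharged alive?** Survival of 78–91% at 30 days means 9–22% dead. Assume that the 5% in-hospital deaths fall within this. Then 4–17% of those randomised, or 4/95 = 4.2% to 17/95 = 17.9% of those discharged, die after discharge with a score of at most 30. With all other discharged participants at a constant 82 and these deaths at 30, the most favourable case, SD ≥ √(0.0421 × 0.9579) × (82 − 30) = 10.4 (11.0 for 85). At 17.9% the bound is 19.9 (21.1 for 85). So SD 5 can describe at most participants who do not die.

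**Power of the planned test.** Simulated Wilcoxon-Mann-Whitney power at 63 per arm, 20,000 trials per cell, whole days, tie-corrected. Assumptions that the SAP does not give: 85/82 and SD 5 are survivor values; total mortality is equal in the arms; the first 5% of deaths score 0; further deaths score uniformly on 0–25 or 0–80 days (this choice moves power by about 1 point at most).

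| Survivor shape | 0% deaths | 5% | 9% | 15% | 22% |
|---|---|---|---|---|---|
| Normal capped at 90 | 90 | 83 | 76 | 63–64 | 49–50 |
| Capped normal, recalibrated to 85/82 and SD 5 | 94 | 88 | 82 | 70–71 | 55–56 |
| Scaled beta | 98.5 | 96 | 92 | 83–84 | 69 |
| Reflected gamma | 99 | 97 | 93 | 85 | 70–71 |
| Reflected lognormal | 99.9 | 99 | 97–98 | 92–93 | 81 |

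The first row departs from the plan's inputs: capping pulls the means to 84.6/81.9 and the SDs to 4.3/4.8, a difference of 2.7 days.

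For reference only, a t-test on the endpoint as scored (difference 2.85 to 3 days, SD 18.5 to 19.5) would have 13–15% power. No t-test is planned, and that figure does not carry over to the rank test.

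**The case against.** The strongest reply is that the SD is largely beside the point for a rank test, and that the plan's own expectations favour it. A mean of 85 on a scale ending at 90 suggests left skew, the SAP anticipates non-normality, and all three left-skewed shapes exceed 90% at both 5% and 9% deaths. The lowest row of the table does not match 85/82 and SD 5; among shapes that do, the floor at 5% deaths is 88%, close to the small loss the SAP allows for. This stands, and it is why no gross shortfall is claimed. It does not supply the missing calculation: the SAP examines neither survivor shape nor mortality, and its allowance concerns the choice of test, not deaths scored 0.

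Second, the 4–17% figure subtracts one literature estimate from another. The SAP calls the survival data limited, and its 30-day clock is ambiguous. That is fair, and the nesting of the 5% is an assumption. If the 78–91% instead refers to discharged patients, however, 9–22% of them die later and the bound rises to √(0.09 × 0.91) × 52 = 14.9 or more.

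Third, equal total mortality is also an assumption, since Sample Size fixes equality only for in-hospital deaths. A treatment effect on later mortality would change the right-hand columns.

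Finally, the protocol may explain how the 5% was used. That would settle the origin of 126, but not the conflict between SD 5 and the scoring, which lies within the SAP.

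**Conclusion.** The point holds. An SD of 5 is incompatible with 5% of participants scored 0. The endpoint's SD is about 18.5 to 19.5 if deaths total 5%, and larger if further deaths occur as the SAP expects. The 90% was calculated for a different variable and a different test, so it is unsupported for the primary analysis, though not shown to be too high at 5–9% deaths.

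Under the assumptions listed, rank-test power over the five shapes is 83–99% at 5% deaths, 76–98% at 9%, 63–93% at 15% and 49–81% at 22%. Only at 22% does every shape tried fall below 90%; other shapes could differ. The contradiction itself needs only the SAP's figures. The power ranges depend on survivor shape, equal mortality and the scoring of later deaths. This should be fixed, but it does not threaten the design.

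**What to change.** Leave the 126 participants, the endpoint and the test unchanged. In Sample Size:

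1. State which participants the means of 85 and 82 and the SD of 5 describe. They cannot describe everyone randomised, nor everyone discharged alive if later deaths occur at the expected rate.
2. State how the 5% in-hospital mortality entered 126. If it was an attrition inflation, say so, and say that these deaths are in fact analysed as 0.
3. Keep the t-test calculation as the design rationale. Beside it give, as the power for the primary analysis, simulated Wilcoxon-Mann-Whitney power for the endpoint as scored. Use design assumptions only and no trial data, mortality from 5% to 22%, and at least one normal and one left-skewed shape bounded at 90. Put the shape, the mortality in each arm and the scoring of later deaths next to each figure.
4. Replace the closing sentence about a small loss of power with that conditional range.

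The cost is a few sentences and one short simulation, with no extra patients. The price is that a single 90% becomes a range that may look less favourable.

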## Statistical interim analysis and stopping guidance

No statistical interim analysis will be performed. There is no stopping guidance since the intervention and comparator are already standard treatments with well-known complications and adverse effects.

## Adherence and protocol deviations and Randomization errors

The intervention and comparator in this pragmatic trial are two treatment strategies: referral to up-front thoracentesis in addition to pharmacological therapy compared with pharmacological therapy alone.

Compliance with the protocol is defined as the participant in the intervention arm being referred to upfront thoracentesis by the treating physician (scheduling when the thoracentesis will be performed). There is the possibility that the physician performing the procedure does not find enough pleural fluid to safely perform the thoracentesis. This case will not be considered a violation of the protocol. In the control group, participants receiving pharmacological treatment alone for five days after randomisation are considered compliant with the protocol.

Major protocol deviation is defined as patients randomised despite violating eligibility criteria. This is considered a randomisation error. Such cases will remain in the trial and have data collected. The ineligible participant will be included in the full analysis dataset because it is our perception that exclusions cannot be made in an objective and unbiased manner due to the unblinded nature of the trial, with a risk of introducing bias post-randomization [8]. The allocated treatment strategy is stopped if the reason for ineligibility means that commencing or continuing treatment is inappropriate or potentially unsafe (e.g. participants randomised despite an indication for diagnostic thoracentesis must be referred to thoracentesis; participants randomised despite a spontaneous bleeding disorder and therefore cannot undergo thoracentesis). Such cases will be analysed according to the allocated treatment arm in accordance with the intention-to-treat principle.

